Background: In recent years, various methodologies have been introduced to enhance the outcomes of scaling and root planing (SRP), with the intent of potentially eliminating the necessity for periodontal surgical interventions under specific circumstances. Noteworthy among these novel approaches are the utilization of non-steroidal anti-inflammatory drugs (NSAIDs) and herbal remedies like Aloe Vera. This present study endeavors to clinically assess the impact of flurbiprofen gel in contrast to Aloe Vera gel, as supplementary agents to SRP, in the elimination of periodontal pocket depths among individuals afflicted by stage III chronic periodontitis, particularly focusing on the subset of smoking patients. **Materials and Methods:** In this study, 60 patients with stage III/grade C periodontitis were enrolled. They were divided into three groups using the split mouth method: Group one (G1), which received Flurbiprofen and placebo, Group two (G2), which received Aloe Vera and placebo, and Group three (G3), which received Flurbiprofen and Aloe Vera. At the baseline, the fourth, eighth-, twelfth weeks and six months following treatment, the plaque index (PI), gingival index (GI), bleeding on probing (BOP), clinical attachment level (CAL), and probing depth (PD) were all measured. **Statistical Analysis:** Statistical analysis was done using SAS 9.4 Software (SAS Institute Inc., Cary, NC, USA). Means and standard deviations (SD) were calculated for all continuous variables (periodontal parameters: CAL, PD, BOP, GI, PI) at the baseline, fourth week, eighth week, and twelfth week and 6 months.

Keywords: periodontitis, flurbiprofen, aloe vera, root planing.

Introduction:

Inflammation and periodontal tissue destruction is a consequence of periodontal pockets originating from chronic periodontitis. [1] The latter is an infectious disease resulting from the interaction between the invasion of biofilm microorganisms and periodontal immune response in a vulnerable host. [2]

During periodontal attachment loss, PGE2 production levels primarily by macrophages and fibroblasts are increased in the tissues and gingival crevicular fluid (GCF). [3,4] PGE2 promotes the release of MMPs, in addition to osteoclastic bone resorption, and it play a significant role in the alveolar bone loss observed in periodontitis. [5]

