30] Aloe Vera also inhibits the cyclooxygenase pathway, dropping the production of prostaglandins, thus decreasing the inflammation. [31]

Some studies stated the use of aloe Vera in dentistry in numerous areas like disinfecting dental unit water network, [32] gutta-percha sterilization, [33] antiseptic effect on candida albicans, [34] Aphthous stomatitis management, [35] as an ingredient in toothpastes [36-37] and mouthwashes.[28] Up to date, limited studies have been reported in relation to the effect of topical application of aloe Vera in the periodontal pocket for periodontal disease management. [38]

The null hypothesis is that flurbiprofen has no statistically significant effect in comparison to Aloe Vera gel as an adjunctive to SRP in the reduction of periodontal pockets in smoking patients with chronic periodontitis stage III.

Aim of this study:

This study aims to evaluate clinically the effect of flurbiprofen gel in comparison to Aloe Vera gel as adjunctive to SRP in the reduction of periodontal pockets in patients with chronic periodontitis stage III in smoking patients.

Materials and methods:

Participants:

This study was conducted at the Department of Oral Surgical Sciences, Division of Periodontology, Faculty of dentistry, Beirut Arab University (BAU)-Lebanon after approval of Institutional Review Board (IRB) with trial NO 2022-H-0100-D-R-0487. Patients were first briefed about the study and written consent was obtained. The study was performed in compliance with the principles of the Declaration of Helsinki.

The estimated sample size will be calculated according to <http://epitools.ausvet.com.au/>, by taking the means of clinical attachment level at 3 months in both groups from a previous similar study conducted by (39) where mean for test site = 5.75 ± 0.35 and mean for control site is = 6.4 ± 0.3 , where the variance will be calculated to be 0.35, assuming a confidence level of 95% and a study power of 80%. The calculated sample size will be 14 patients per group (28 operating sites). However, as some dropouts may be expected, a minimum of 20 patients per group were recruited

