Inclusion criteria: 60 patients were selected who had clinical periodontal loss and radiographic bone loss of stage III/grade C with no history of systemic disease. They had at least 2 periodontal sites with a pocket depth of six mm or greater, radiographic evidence of bone loss extending to the middle third of the root, and clinical attachment loss of five mm or more. Eligible subjects were categorized as current smokers if they consistently smoked more than 10 cigarettes per day for a minimum of 5 years. Additionally, individuals with no record of undergoing any periodontal treatment within the six months preceding the study were considered for inclusion. These stringent criteria aimed to ensure a relevant and homogeneous patient cohort for the research investigation.

Exclusion criteria: Patients with systemic illnesses such as diabetes mellitus or conditions that could potentially impair wound healing were excluded from participation. Additionally, individuals who were pregnant or lactating were not considered for inclusion in the study. Subjects who had been prescribed systemic antibiotics or non-steroidal anti-inflammatory drugs (NSAIDs) within the three months preceding the study were also excluded. Furthermore, individuals with confirmed or suspected hypersensitivity to Flurbiprofen or aloe Vera, the focus of the investigation, were not included in the study population. These stringent exclusion criteria aimed to control for potential confounding factors and establish a well-defined and relevant patient group for the research analysis.

Clinical protocol

Initial therapy was performed on all patients and consisted of full mouth scaling and root planing on 2-4 sessions, by hand and ultrasonic instrumentation, with oral hygiene instructions reinforcement and proper brushing technique (modified Bass technique) instructions. Note that patients received the same toothbrushes, toothpaste, and interdental brushes. Oral hygiene was reinforced at every visit.

The selected patients were allocated into three groups (each containing 20) with the help of a computerized randomizer (Randomizer.org), and using a split mouth design, sites were randomly allocated for each patient into either test or control group using a coin flip method:

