Initially, the PI and GI were measured at four sites per tooth, with gingival bleeding being recorded within 15 seconds. To prevent misinterpretation of gingival bleeding as BOP, patients were asked to rinse with water after this assessment. Subsequently, all teeth were probed at six different locations per tooth. CAL was determined as the distance from the cemento-enamel junction (CEJ) to the pocket depth, while the PD was measured as the distance from the gingival margin to the base of the pocket. BOP was recorded 15 seconds after probing. It is important to note that these clinical parameters were recorded at the baseline (1st visit) before the treatment and were repeated at the fourth week (2nd visit), eighth week (3rd visit), twelfth week (fourth visit), and at 6 months (5th visit). During this observation period, participants received reinforcement of plaque control and additional instructions to maintain optimal oral hygiene

Preparation of gels:

Aloe Vera:

Aloe vera gel used in this study was 98% aloe vera[®] gel concentration (Avivir; Denmark) and 2% normal saline. Commercial preparation method of 98% concentration of aloe vera gel was washing the ripe aloe Vera leaves thoroughly under water and cutting off their skin. Each leaf was cut into several pieces and seeping gel from the pieces were collected in a sterile container and stored at 4°C until the time of application. [38]

Flurbiprofen:

Gel was made of 20% poloxamer and 10% ethanol as an Optimum formulation with sustained release up to 48 hours and a reasonable sol gel transition phase.

Statistical analysis:

Statistical analysis was done using SAS 9.4 Software (SAS Institute Inc., Cary, NC, USA). Means and standard deviations (SD) were calculated for all continuous variables (periodontal parameters: CAL, PD, BOP, GI, PI) at the baseline, fourth week, eighth week, and twelfth week and 6 months. Repeated linear mixed-effects models (PROC MIXED in SAS) were used to examine the changes in all periodontal parameters over the five-time points within each group and between groups. An unstructured covariance matrix was used, residual plots were visually reviewed to check model fit, and extreme outliers were eliminated using the restricted likelihood distance. A Tukey-Kramer 8 correction was applied to all pairwise comparisons. One-way ANOVA was used to examine group differences in PD reduction and CAL. A p-value of 0.05 was considered statistically significant.

References:

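### The one-way ANOVA defines no unit, factor or flurbiprofen-minus-aloe contrast; if its factor is G1-G3 and both sites of each patient enter, its overall F does not test the stated null

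*Combined protocol and SAP*

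**What the plan says.** The hypothesis, at the end of the Introduction, is a comparison of two treatments: "The null hypothesis is that flurbiprofen has no statistically significant effect in comparison to Aloe Vera gel as an adjunctive to SRP".

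The Clinical protocol section uses the word group in two senses. One is patient sets: "The selected patients were allocated into three groups (each containing 20" patients). In the same sentence, the sites within each patient are assigned by coin flip to a test or a control group. The group descriptions then make each patient set a pair of site treatments:

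- G1: flurbiprofen on one side, SRP on the other.
- G2: aloe vera on one side, SRP on the other.
- G3: flurbiprofen on one side, aloe vera on the other. Neither side is called test or control.

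The Abstract differs on the comparator. It has "Group one (G1), which received Flurbiprofen and placebo", while the Clinical protocol describes SRP alone as the G1 control. On the third set the two places agree: "Group three (G3), which received Flurbiprofen and Aloe Vera".

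The Statistical analysis section plans PROC MIXED models for change over the five visits inside and across groups, a Tukey-Kramer correction for pairwise comparisons that it does not list, and then: "One-way ANOVA was used to examine group differences in PD reduction and CAL". It gives no unit, factor levels, visit or contrast for that ANOVA.

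**The concern.** The question is flurbiprofen against aloe, but a test of whether G1, G2 and G3 differ answers something else whenever SRP sites enter the response. Two of the three sets contain an SRP site and G3 does not. If both gels work equally well, G3 still differs from G1 and G2, because it swaps the SRP site for a second gel site. A small F-test p-value would then reflect gel against SRP, and it could be reported as a difference between the gels.

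The rest of the section does not settle the matter. The mixed model is described without a site-treatment or side term, and no pair under Tukey-Kramer is identified as the gel contrast. The paired comparison inside G3, the only within-patient comparison of the two gels, is not specified.

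**Working it through.** **Inputs from the plan (Participants, sample size).** "where mean for test site = 5.75 ± 0.35 and mean for control site is = 6.4 ± 0.3", so the difference is 6.4 − 5.75 = 0.65 mm in attachment level at 3 months. The stated variance is 0.35, with 95% confidence, 80% power and 20 patients recruited per set.

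**The plan's own figure.** n = 2(z₀.₉₇₅ + z₀.₈₀)² × 0.35 / 0.65² = 13.004 with unrounded z values, which rounds up to the stated 14. Reading 0.35 as an SD gives 5, so the plan did use 0.35 as a variance.

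**Assumptions that are not in the documents.** One site per side; correlation ρ between a patient's two sites of 0.25/0.5/0.7; each gel 0.65 mm better than SRP; variance 0.35 for whichever response is analysed. The 0.65 mm is borrowed from the test-versus-control inputs above. The plan states no expected difference between flurbiprofen and aloe.

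**Overall F by G1-G3 when the gels are equal (the stated null is true).** The noncentrality is λ = 20 Σ(mᵢ − m̄)² / variance, with 2 and 57 df.

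- *Patient means.* Expected benefits over SRP are 0.325, 0.325 and 0.65, so 20Σ(mᵢ − m̄)² = 1.408. The variance is 0.35(1+ρ)/2 = 0.219/0.263/0.298 and λ = 6.44/5.37/4.73. Rejection: **59/51/46%**.
- *Within-patient differences.* Expected values are 0.65, 0.65 and 0, so 20Σ(mᵢ − m̄)² = 5.633. The variance is 2 × 0.35(1−ρ) = 0.525/0.35/0.21 and λ = 10.73/16.10/26.83. Rejection: **82/95/99.7%**.
- *All sites pooled as independent.* By simulation, rejection is about **62-64%**.
- *Gel sites only* (G3 entering by its flurbiprofen site or by the mean of its two sites). By simulation, rejection is about **5%**, so on this reading the F does address the null.

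If 0.35 were an SD, λ would be 0.35/0.1225 = 2.86 times larger on the first two readings, and their rejection rates would be higher.

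**The G1-G2 pair.** When the gels are equal its expected value is zero, so it is not biased toward a false gel difference. Its power when flurbiprofen is truly 0.65 mm better than aloe depends on the response (57 df, critical value 2.00 unadjusted and 2.41 with Tukey):

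| Response | Estimates | Standard error | Power, unadjusted | Power, Tukey |
|---|---|---|---|---|
| Patient mean | half the gel effect, 0.325 mm | √(0.35(1+ρ)/20) | 58/50/46% | 42/35/31% |
| Within-patient difference | the full effect, since (F−SRP) − (A−SRP) = F−A | √(4 × 0.35(1−ρ)/20) | 80/93/99% | 67/85/98% |

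With sites pooled as independent, the pair also carries a wrong standard error. If neither gel beats SRP, its unadjusted type I error is 8/11/13%.

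**Information left unused.** Variance of flurbiprofen minus aloe, per unit of site variance:

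- Joint model on all 60 patients: (1−ρ²) / [10(2+ρ)] = 0.042/0.030/0.019.
- G3 pairs alone: 2(1−ρ)/20 = 0.075/0.050/0.030, which is 1.8/1.7/1.6 times the joint model.
- G1 against G2 test sites: 2/20 = 0.10, which is 2.4/3.3/5.3 times.
- G1 against G2 within-patient differences: 4(1−ρ)/20 = 0.15/0.10/0.06, which is 3.6/3.3/3.2 times.

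**The case against.** The best defence is that the ANOVA is a secondary line in a section that also plans between-group mixed models and corrected pairwise comparisons. Nothing in the plan says that the overall F will be read as a gel contrast, and sound readings of the ANOVA exist. That is fair, and it rules out several stronger statements that a reader might infer:

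- *That any G1-G3 factor makes the F irrelevant.* It does not if only gel sites enter. But the Clinical protocol names no test site in G3, so this reading needs a rule that is not in the plan.
- *That a one-way ANOVA cannot use the pairing.* It does if the response is the within-patient difference, and the G1-G2 pair then estimates the full gel effect. The overall F on that response is nonetheless the most misleading of the readings.
- *That G3 is the only direct comparison of the gels.* Patients were randomised among the three sets, so G1 against G2 test sites is also a randomised comparison. G3 is the only within-patient one.
- *That the trial is underpowered for a planned gel difference.* No such difference is planned. The 0.65 mm comes from a cited study of locally delivered minocycline in smokers. Even on that borrowed figure, G1 against G2 test sites has 92% power, and G3 pairs have 97/99.6/over 99.9%.
- *That the ANOVA is the sole test of the hypothesis, or that PROC MIXED is wrong.* The documents say neither.

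What stands is that the section nowhere names the contrast that answers its own null, and that three natural readings of the ANOVA give an F that does not test it.

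**Conclusion.** The point holds, with a condition. The unit, the factor and the gel contrast of the ANOVA are undefined. If the factor is G1-G3 and both sites of each patient enter, as a mean, a difference or pooled sites, the overall F responds to gel against SRP. With equal gels it rejects in roughly half to nearly all trials on the assumptions stated. The exact rates depend on the borrowed 0.65 mm, the variance of 0.35 (given for attachment level, not for pocket-depth reduction), one site per side and the assumed correlations. The direction depends only on G3 having no SRP site and on the gels doing better than SRP.

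The harm lies in misreading that p-value and in losing precision. The G1-G2 pair does not create a spurious gel difference, but it leaves out G3 and, on patient means, shows only half the effect. No reading of the ANOVA examined here uses all the information on flurbiprofen against aloe.

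**What to change.** For the flurbiprofen-aloe question, use one site-level PROC MIXED on all 60 patients:

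- **Fixed effects:** site treatment (flurbiprofen, aloe, SRP control), visit and their interaction.
- **Correlation:** patient as subject, with the link between the two sides modelled. Examples are UN@UN over side and visit, or a random patient effect with a visit covariance for site within patient. State how several sites on one side are handled.
- **Main contrast:** flurbiprofen minus aloe in change from baseline, at one visit fixed in advance. Report each gel minus SRP from the same model.
- **Check:** the paired contrast inside G3.
- **Assumption to state and examine:** treatment on one side does not affect the other side. Compare the gel estimates from G1 and G2 with those from G3.

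If the ANOVA is kept, define its unit, factor and visit, label it supportive, and do not interpret its overall F as a comparison of the gels.

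The Abstract (placebo) and the Clinical protocol (SRP control) must be reconciled before the treatment factor is coded.

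The cost is SAP wording and one model re-specification, with no new patients, visits or measurements. The covariance is slightly larger: UN@UN over 2 sides and 5 visits has 3 + 15 − 1 = 17 parameters, against 15 for an unstructured matrix over 5 visits. The joint model also relies on there being no effect across sides.

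### The one-way ANOVA of PD reduction and CAL has no baseline covariate; adding the site's own baseline value is a cheap, modest gain in precision

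*Combined protocol and SAP*

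**What the plan says.** The Statistical analysis section gives two between-group analyses.

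- The first is a mixed model: repeated linear mixed-effects models with unstructured covariance "were used to examine the changes in all periodontal parameters over the five-time points within each group and between groups". Baseline is one of the five responses. The fixed effects are not listed.
- The second is the ANOVA: "One-way ANOVA was used to examine group differences in PD reduction and CAL". No covariate and no visit are named. The sentence can be read as PD reduction plus CAL level, or as reduction in both.

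The section does not say which analysis is primary.

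The adjusting variable exists: under Clinical measurements, "these clinical parameters were recorded at the baseline (1st visit) before the treatment". The sample size paragraph (Participants) treats CAL as a level, "by taking the means of clinical attachment level at 3 months in both groups", with "mean for test site = 5.75 ± 0.35 and mean for control site is = 6.4 ± 0.3". On allocation, Clinical protocol puts 20 patients in each of three groups, and within patients "sites were randomly allocated for each patient into either test or control group using a coin flip method". The aim is the "effect of flurbiprofen gel in comparison to Aloe Vera gel as adjunctive to SRP in the reduction of periodontal pockets".

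**The concern.** A one-way ANOVA has a grouping factor and nothing else. On a level, it ignores the part of the outcome that baseline predicts. On a change score, it fixes the baseline slope at 1, whereas a covariate model estimates that slope. Either way, residual variance can be larger than necessary, and part of any chance baseline imbalance passes into the estimate.

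With groups of 20, and no stratification by baseline severity described, such imbalance is not rare between patient groups. The aim compares two active gels, whose difference may be smaller than the test-versus-control difference used for sizing. Precision would matter most there.

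**Working it through.** **Inputs from the documents (Participants, Clinical protocol).** Difference in 3-month CAL: 6.4 − 5.75 = 0.65 mm. The stated variance of 0.35 gives SD √0.35 = 0.592 mm. The printed site SDs pool to √((0.35² + 0.30²)/2) = 0.326 mm. There are three groups of 20. Two-sided alpha of 0.05 is used; sidedness is not stated.

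**Assumed, not in the documents.** r = 0.3 to 0.8. k, the baseline SD divided by the follow-up SD, is 1 or 0.7; the entry limits ("at least 2 periodontal sites with a pocket depth of six mm or greater") may narrow the baseline spread, and may also lower r. The CAL SD is used for PD as well.

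**The plan's own figure.** 2 × 0.35 × (1.960 + 0.842)² / 0.65² = 13.004, rounded up to 14 per group. The stated 14 is reproduced.

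**Variance factors, with follow-up SD = 1 and baseline SD = k**

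- Raw level: 1
- Change score: 1 + k² − 2rk
- Baseline as covariate (ANCOVA): 1 − r²
- Change minus ANCOVA: (k − r)², which is zero at r = k

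| r | ANCOVA / level | ANCOVA / change, k = 1 | ANCOVA / change, k = 0.7 |
|---|---|---|---|
| 0.3 | 0.91 | 0.65 | 0.85 |
| 0.5 | 0.75 | 0.75 | 0.95 |
| 0.7 | 0.51 | 0.85 | 1.00 |
| 0.8 | 0.36 | 0.90 | 0.97 |

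With equal SDs the two gains are the same at r = 0.5. A level gains more above that value and a change score gains more below it.

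**Cost of estimating the slope.** Three groups: 1 + 1/(60 − 3 − 2) = 1.018. Two groups of 20: 1 + 1/(40 − 2 − 2) = 1.028. For a level in the three-group model, adjustment breaks even at r = √(1 − 1/1.018) ≈ 0.13.

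**Power: noncentral t, 20 against 20, 38 df (ANCOVA 37 df, variance × 1.028)**

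| Difference, SD | Analysis | Unadjusted | ANCOVA |
|---|---|---|---|
| 0.65 mm, 0.592 | Level | 92% | 94% (r = 0.3), 97% (r = 0.5) |
| 0.65 mm, 0.592 | Change, r = 0.3, k = 1 | 82% | 94% |
| 0.65 mm, 0.326 | Either | at least 99.9% | at least 99.9% |
| 0.325 mm, 0.592 | Level | 40% | 42% (r = 0.3), 49% (r = 0.5), 65% (r = 0.7) |
| 0.325 mm, 0.592 | Change, r = 0.3, k = 1 | 30% | 42% |
| 0.325 mm, 0.592 | Change, r = 0.7, k = 0.7 | 66% | 65% |

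The 0.325 mm rows take half the planning difference as an illustration of a gel-versus-gel contrast; the documents give no such figure. Using the 57 error df of the three-group ANOVA (56 after adjustment) moves these powers by about 1 point.

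**Chance imbalance.** The probability of a baseline difference of 0.5 SD or more is 2 × (1 − Φ(0.5/√(2/20))) = 11% between independent groups of 20. Within patients, with an assumed between-site correlation of 0.5, it is 2 × (1 − Φ(0.5/√(2 × 0.5/20))) = 2.5%. At SD 0.592, a 0.5 SD imbalance shifts a level by 0.5 × r × 0.592 = 0.09 to 0.24 mm. With k = 1 it shifts follow-up minus baseline by 0.5 × (r − 1) × 0.592 = −0.21 to −0.06 mm. For PD reduction (baseline minus follow-up) the signs reverse.

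**The case against.** Several counter-arguments have force.

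- **PD reduction already uses baseline.** This stands. A reader might infer that the ANOVA ignores baseline for both outcomes. For PD only the estimated slope is missing, and when r is close to k there is nothing to gain.
- **CAL does not necessarily gain more than PD.** This stands. Treating CAL as the outcome that benefits assumes that it is analysed as a level, which the plan does not say, and that r exceeds 0.5. At r = 0.3 with equal SDs the variance falls by 9% for a level and by 35% for a change.
- **The mixed model already contains baseline.** This stands in part. Baseline enters as a response, and because the fixed effects are unlisted one cannot assert that adjustment is absent, only that none is specified. If baseline means are left free, the group-by-time contrast is close to a comparison of changes, so this model does not by itself give the full gain.
- **The benefit is conjectural.** This stands in part. For the only effect size in the documents, power is already 92% on levels at SD 0.592 and higher at SD 0.326. The larger gains depend on assumed values of r, k and the difference. Within-patient contrasts, including the two gels in Group three, are less exposed to imbalance.

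**Conclusion.** The point holds as a low-severity efficiency improvement. The ANOVA as written has no baseline covariate, the baseline values are available, and the mixed model is not specified in a way that closes the gap.

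Over r = 0.3 to 0.8 the variance saving before slope cost is 9% to 64% for a level. For a change score with equal SDs it is 35% to 10%, falling to nil where r is near k. The size rests wholly on r and k, which the documents do not give.

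A reader might infer that the unadjusted ANOVA is biased or its test invalid. The documents do not support that on this point: patients are allocated by a computerised randomiser and sites by coin flip, so omitting baseline costs precision and leaves chance imbalance uncorrected, but does not bias the comparison.

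**What to change.** Replace the ANOVA with a model of follow-up PD and of follow-up CAL at a named visit. Include the site's own baseline value as a covariate, with baseline-by-visit terms if several visits are modelled, and a patient random effect where both sites of a patient enter. Alternatively, constrain treatment means to be equal at baseline in the mixed model, again with a patient effect. Apply the same rule to PD and CAL. With the baseline covariate included, the estimated treatment effect is the same whether the outcome is expressed as a level or as a change (apart from sign for a reduction), so the ambiguity over CAL no longer affects the result.

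The cost is a small change to the SAS model and one extra parameter: about 1.8% in variance for three groups, or about 3% for a comparison of two groups of 20. This can slightly outweigh the gain for a change score when r is near k. No new data or design change is needed. The methods are written in the past tense; if results have been seen, label the adjusted analysis post hoc and report it beside the original ANOVA.

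### Group differences in PD and CAL are tested twice, and the one-way ANOVA can use only patients measured at an unnamed visit, while the planned mixed model also uses the earlier visits of those who withdraw

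*Combined protocol and SAP*

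**What the plan says.** The Statistical analysis section of the combined protocol and SAP sets out two analyses that overlap.

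- The first is a mixed model: "Repeated linear mixed-effects models (PROC MIXED in SAS) were used to examine the changes in all periodontal parameters over the five-time points", applied both within and between groups. On its covariance the plan says "An unstructured covariance matrix was used". PD and CAL are among the parameters covered.
- The second is separate: "One-way ANOVA was used to examine group differences in PD reduction and CAL".

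For the ANOVA the section names no visit, no analysis set and no treatment of missing values. It does not rank the ANOVA against the mixed model.

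The sample-size paragraph (Materials and methods, Participants) arrives at 14 per group and then adds: "However, as some dropouts may be expected, a minimum of 20 patients per group were recruited". It gives no dropout rate. No imputation is described anywhere. Measurements are scheduled at baseline, weeks 4, 8 and 12, and 6 months (Clinical measurements).

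**The concern.** A reduction in PD can be calculated only for a patient with both a baseline value and a value at the visit analysed. With no imputation planned, the ANOVA therefore omits anyone missing at that visit. If the visit is 6 months, a patient who leaves after week 12 drops out of the comparison although weeks 4, 8 and 12 were recorded. The likelihood-based mixed model keeps that patient's recorded visits.

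Two things follow. First, the report could carry two p-values for the same contrast, based on different patients, with no rule for which to believe. Second, if patients with a poor early response are more likely to leave, the arm doing worse loses more of its poor responders, and the difference among those who remain shrinks. Pocket reduction is the outcome in the stated aim and null hypothesis, so this ambiguity touches the trial's main question.

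**Working it through.** **Inputs from the plan.** The sample-size paragraph quotes, from an earlier study, "mean for test site = 5.75 ± 0.35 and mean for control site is = 6.4 ± 0.3", a difference of 6.4 - 5.75 = 0.65 mm. It uses a variance of 0.35 (SD = √0.35 = 0.592), 95% confidence and 80% power. Significance is at 0.05, taken here as two-sided. The variance is used as the plan states it; whether 0.35 is the right value is a separate matter.

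**Reproducing the plan's figure.** n per group = 2(1.960 + 0.842)² × 0.35 / 0.65² = 13.004, rounded up to 14. This matches.

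**Dropout margin.** (20 - 14)/20 = 30%. This is the most the recruited number tolerates, not a rate the plan states.

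**Power from numbers alone** (normal approximation, power = Φ(0.65/√(2 × 0.35/n) - 1.96)):

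| Patients per group at the visit | Power |
|---|---|
| 20 | 93.5% |
| 18 | 90.9% |
| 16 | 87.4% |
| 14 | 82.8% |

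The planned number absorbs a purely random loss of up to 30%.

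**Assumptions for the simulations.** There are 20 patients per arm, two arms compared between patients, and a true difference of 0.65 mm. Dropout falls between week 12 and 6 months and the ANOVA is done at 6 months. Dropout rate, correlation between visits and strength of dependence are not in the documents, so ranges are shown. The likelihood estimate stands for the planned mixed model.

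**Random dropout** (five visits; variance 0.35 at each visit; correlation 0.3-0.9 constant across visits, or first-order autoregressive at 0.8). Both estimates are unbiased. Ratio of the ANOVA's SE to the mixed model's:

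- 10% dropout: from 0.233/0.231 = 1.01 (constant 0.3) to 0.216/0.210 = 1.03 (autoregressive), so 1-3% larger.
- 30% dropout: from 0.174/0.168 = 1.04 (constant 0.7) to 0.247/0.221 = 1.12 (autoregressive), so 4-12% larger.

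**Dropout depending on observed week-12 response** (two-visit model; the reduction has variance 0.35; correlation between week 12 and 6 months 0.5-0.8; 30% dropout overall):

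| Dependence (log-odds per SD) | Dropout, worse vs better arm | ANOVA difference | Likelihood difference |
|---|---|---|---|
| Moderate (1) | about 40% vs 20% | 0.58-0.61 mm | about 0.65 mm |
| Strong (2) | about 44% vs 16% | 0.50-0.56 mm | about 0.65 mm |

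As a share of 0.65, the shrinkage is 6-11% (0.04-0.07 mm) under moderate dependence and 14-23% (0.09-0.15 mm) under strong dependence.

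**Wider range.** The five-visit model with strong dependence and 10-30% dropout gives ANOVA differences from 0.635 mm (10%, constant correlation 0.9) down to 0.478 mm (30%, autoregressive 0.8). The likelihood estimate stays at 0.642-0.657 mm. At the worst value with 14 per group, power is Φ(0.478/√(2 × 0.35/14) - 1.96) = Φ(0.18), about 57%. In these response-dependent cases the two SEs are nearly equal, so the cost is bias rather than precision.

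**No dropout.** The two analyses give the same estimate.

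**The case against.** The strongest reply is that the better analysis is already in the plan: the mixed model is to "examine the changes in all periodontal parameters over the five-time points within each group and between groups", which includes PD and CAL between groups. A reader might infer that the trial's test of pocket reduction is restricted to completers. The documents do not support that, because nothing makes the ANOVA the deciding test. Nor is it tied to 6 months. The sample size rests on CAL at 3 months, and at a week-12 ANOVA the dropout simulated here would remove nobody. This stands, but nothing makes the mixed model decisive either.

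A reader might also take 30% as the plan's expected dropout. It is only what moving from 14 to 20 allows, and the text describes 60 patients without reporting losses. The strong case also needs about 44% against 16% dropout by arm, and nothing in the documents points to such a gap.

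The split-mouth design limits the point further. Gel against SRP alone in G1 and G2, and flurbiprofen against Aloe Vera in G3, are within-patient contrasts, and a patient who leaves takes both sites. In a check with strong dropout on the patient's mean response, the paired difference stayed at 0.649-0.652 mm. The bias therefore concerns comparisons between patients in different groups. For those, 0.65 mm is borrowed from a test-versus-control site difference. A smaller true difference gives less bias, and with equal arms and the same dropout mechanism there is none. The modelled error is attenuation, not a spurious finding.

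Finally, the mixed model's advantage depends on data being missing at random. All these limits stand. They narrow the point without removing it, because the ANOVA still uses less of the recorded data for the same contrast.

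**Conclusion.** The point holds in a limited form. The plan analyses group differences in PD and CAL twice, by methods that treat withdrawn patients differently, expects withdrawals, and does not say which result stands.

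The size depends on facts the documents do not give. It is nil with no dropout. With random dropout it is a modest loss of precision that the recruited number absorbs. If dropout follows earlier observed response and so differs between arms, the between-patient difference is attenuated by roughly 0.04-0.07 mm of 0.65 mm under moderate dependence and 0.09-0.15 mm under strong dependence. Those figures assume 30% dropout after week 12, an ANOVA at 6 months and a visit correlation of 0.5-0.8. They illustrate what could happen and do not predict this trial's result. Because a method that avoids the problem is already planned, the change is worth making.

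**What to change.** In the Statistical analysis section, replace the one-way ANOVA with contrasts of change from baseline in PD and CAL at a named visit, estimated from the mixed model already planned (for example with LSMEANS or ESTIMATE statements). Include all randomised patients and all measurements up to withdrawal, and state the missing-at-random assumption.

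If the ANOVA is kept, label it a supportive analysis of patients measured at that visit, and report beside it the patients and sites lost by group and visit.

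The cost is SAP wording and a few contrast statements, with no new patients, visits or data. The small downside is reliance on missing at random: dropout driven by deterioration that no visit recorded would still bias both analyses.
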